5.1 Analysis set/populations

Among patients who were enrolled in the study and received maintenance avelumab treatment between 24 February 2021 and 30 November 2021, patients meeting all the inclusion criteria will be analyzed.

5.2 Handling of missing values

An absence of data for analysis will be treated as missing values, and no special imputation processing will be performed using statistical methods.

However, if there are specifications for handling of missing values in subsequent each specification, they are followed.

5.3 Handling of data on the number of days

The number of days from the start date to the target date will be calculated as follows:

- The target date is earlier than the start date = Target date – Start date
- The target date is on or after the start date = Target date – Start date + 1

If the data for "year" and "month" among the date data are missing, no calculation will be performed.

If the data on "day" of the date is missing, data will be substituted by 1.

The number of days in one month is converted to 30.

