7. RATIONALE AND BACKGROUND

[figure not shown]
Bladder cancer accounts for approximately 90% of Urothelial carcinoma (UC). Approximately 550,000 cases of bladder cancer are newly diagnosed worldwide each year¹. Each year, 200,000 cases of death are caused by bladder cancer. Bladder cancer incidence and death rates have not changed by 25 annuals². According to the cancer statistical forecast in 2021 conducted by the National Cancer Center Japan, the estimated number of bladder cancers and deaths in 2021 in Japan were 24,300 and 9,700, respectively³. Patients with metastatic UC have a dismal prognosis with a 5-year survival rate of only 5%. Platinum-based polychemotherapy regimen is currently the first-line (1L) standard of care (SOC) for patients with advanced/metastatic disease, but despite high initial response rates, durable and complete responses following 1L chemotherapy (Cht) are uncommon, and most patients will ultimately experience disease progression within 9 months after initiation of treatment⁴.

CCI

CCI

Avelumab (MSB0010718C, BAVENCIO®) is a human immunoglobulin G1 monoclonal antibody directed against the programmed death ligand 1 (PD-L1). In Japan, Cht is the 1L SOC recommended in guidelines for locally advanced or metastatic UC; CCI

CCI

Avelumab in combination with best supportive care (BSC) as a maintenance treatment had been evaluated versus BSC alone in a Phase 3 randomized trial (JAVELIN Bladder 100) in patients with locally advanced or metastatic UC who had not progressed with 1L platinum-based Cht. The JAVELIN Bladder 100 study has demonstrated a significant 7.1-months improvement in median OS with Avelumab+BSC as 1L maintenance versus BSC alone (median OS, 21.4 months vs 14.3 months), with a 31% reduction of the death risk in the overall population (hazard ratio = 0.69 (95% confidence interval [CI], 0.56, 0.86), p=0.001)⁸. The results of Japanese subgroup analysis in the JAVELIN Bladder 100 were generally consistent with those in the overall population⁹. CCI

The present study, B9991048, aims to evaluate the demographic and baseline disease characteristics and current treatment outcomes in patients with locally advanced or metastatic UC treated with avelumab those who had been prescribed Avelumab in a period of 9 months after launch, and had a follow-up duration of 7 months. In CCI

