9.8.4. Analysis of Secondary Endpoints

Efficacy Endpoints

See 19. For the time-to-event endpoints, eg, TTF and rwPFS, the Kaplan-Meier estimates (product-limit estimates) will be presented together with a summary of associated statistics including the median time with 2-sided 95% CIs. In particular, the survival rate at several timepoints will be estimated with corresponding 2-sided 95% CIs.

Other Secondary Endpoints

See 19. These endpoints will be descriptively summarized. These endpoints will also be displayed graphically, if necessary.

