8.1 Efficacy endpoints

8.1.1 Time to treatment failure (TTF) of avelumab

Target : Analysis set

population

n

Endpoint : Time to treatment failure (TTF) of avelumab

Statistical analysis : For the endpoint, the median and its 95% confidence interval will be calculated using the Kaplan–Meier method. In addition, the Kaplan–

Meier curve will be plotted, and the TTF rate for every 2 months and its 95% confidence interval will be calculated. Greenwood's formula will be used to calculate the confidence interval for the TTF rate.

In order to evaluate the overall observation period of the study, the median observation period will be calculated by estimating the reverse KM curve in which censoring patients are regarded as patients with events and patients with events are regarded as censoring patients.

In addition, as a sensitivity analysis, " interruption due to being well-controlled" will be treated as an event based on the day when death or discontinuation was observed before the date of the last

observation, and if no death or discontinuation or death occurred before the date of the last observation, data will be censored at the date of the last observation.

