8.1.2 Real-world progression-free survival (rwPFS)

Target : Analysis set

population

n

Endpoint : **Real-world progression-free survival (rwPFS)**

Statistical analysis : For the endpoint, the median and its 95% confidence interval will be calculated using the Kaplan–Meier method. In addition, the Kaplan–Meier curve will be plotted, and the rwPFS rate for every 2 months and its 95% confidence interval will be calculated. Greenwood’s formula will be used to calculate the confidence interval for the rwPFS rate.

In order to evaluate the overall observation period of the study, the median observation period will be calculated by estimating the reverse KM curve in which censoring patients are regarded as patients with events and patients with events are regarded as censoring patients.

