8.1.4 Real-world progression-free survival from chemotherapy (rwPFS-c)

Target : Analysis set

population

n

Endpoint : Real-world progression-free survival from chemotherapy (rwPFS-c)

Statistical analysis : For the endpoint, the median and its 95% confidence interval will be calculated using the Kaplan–Meier method. In addition, the Kaplan–Meier curve will be plotted, and the rwPFS-c rate for every 2 months and its 95% confidence interval will be calculated. Greenwood's formula will be used to calculate the confidence interval for the rwPFS-c rate.

In order to evaluate the overall observation period of the study, the median observation period will be calculated by estimating the reverse KM curve in which censoring patients are regarded as patients with events and patients with events are regarded as censoring patients.

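### The 30-day month in SAP 5.3 makes any median reported in months 1.46% too long and reads the 2-monthly rates slightly early from month 4 on

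*SAP*

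**What the plan says.** SAP 5.3 sets the conversion without exception and without listing the variables it covers: "The number of days in one month is converted to 30". The same section counts durations in whole days: "The target date is on or after the start date = Target date – Start date + 1".

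Months then enter the analysis of three endpoints. For TTF (SAP 8.1.1), "the TTF rate for every 2 months and its 95% confidence interval will be calculated"; SAP 8.1.2 and 8.1.4 say the same of rwPFS and rwPFS-c. Each of these sections also asks for a Kaplan–Meier median and for a follow-up figure: "the median observation period will be calculated by estimating the reverse KM curve".

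The medians have no stated unit. SAP 5.5 labels the treatment-free interval and the treatment durations as days but gives none for TTF, rwPFS or rwPFS-c. Protocol 9.8.4 promises only summary statistics "including the median time with 2-sided 95% CIs".

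**The concern.** Twelve 30-day months make 360 days, so a year of 365.25 days counts as 365.25/30 = 12.175 months. Dividing by too small a constant lengthens every duration in months. Placing a landmark at too few days reads the survival curve too early, and since that curve never rises, the rate can only be equal or higher. The error therefore runs in one direction and does not shrink as the sample grows.

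The study has no comparator arm in which the same error would cancel. One of its secondary objectives is to evaluate effectiveness, and the results are meant for publication. Figures in months are likely to be read beside other figures in months, such as those in Protocol section 7 ("median OS, 21.4 months vs 14.3 months").

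**Working it through.** **Inputs.** 30 days per month and whole-day times (SAP 5.3); landmarks every 2 months (SAP 8.1.1, 8.1.2, 8.1.4); index dates from 24 February to 30 November 2021 and observation to 30 June 2022 (Protocol 6). Assumed: a mean calendar month of 365.25/12 = 30.4375 days. The plan contains no calculated result that could be reproduced first.

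**1. Durations in months.** Inflation = 30.4375/30 = 1.0146, or +1.46% (with 365/12 = 30.417 days, +1.39%).
- True 6.0 months: 6 × 1.0146 = 6.09.
- True 12.0 months: 12 × 1.0146 = 12.18.
- True 24.0 months: 24 × 1.0146 = 24.35.

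Confidence limits and the reverse Kaplan–Meier follow-up median scale by the same factor if given in months.

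**2. Where the landmarks fall.** At k months the SAP reads day 30k; the mean month gives day 30.4375k. The last column lists the whole days on which an event would be counted under the second but not the first.

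| Month | SAP day | Mean-month day | Early by (days) | Whole days added |
|---|---|---|---|---|
| 2 | 60 | 60.875 | 0.875 | none |
| 4 | 120 | 121.75 | 1.75 | 121 |
| 6 | 180 | 182.625 | 2.625 | 181–182 |
| 8 | 240 | 243.5 | 3.5 | 241–243 |
| 12 | 360 | 365.25 | 5.25 | 361–365 |

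The curve steps only on whole days, so S(60.875) = S(60) and the 2-month rate is identical under both rules. The 12-month landmark is within reach: 24 February 2021 to 30 June 2022 is 491 days.

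**3. Size of the shift in a rate.** For an assumed exponential curve with median M months, the shift at k months is 0.5^(30k/(30.4375M)) − 0.5^(k/M).

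| Assumed median (months) | Shift at 6 months (points) | Shift at 12 months (points) |
|---|---|---|
| 3 | 0.50 | 0.25 |
| 6 | 0.50 | 0.50 |
| 12 | 0.35 | 0.50 |
| 24 | 0.21 | 0.35 |

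Over all medians and landmarks the maximum is 0.53 points. As a single example, a 180-day median gives 0.5^(360/180) = 25.0% at day 360 and 0.5^(365.25/180) = 24.5% at day 365.25.

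**4. Scale of sampling error.** The sample size is redacted. The 95% half-width at a 50% rate without censoring is 1.96 × √(0.25/n): 13.9 points at an assumed n = 50, 9.8 at 100 and 6.9 at 200.

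**5. Protocol design months.** 30 November 2021 to 30 June 2022 is 212 days: 212/30 = 7.07 and 212/30.4375 = 6.97 months. 24 February to 30 November 2021 is 279 days: 9.30 and 9.17 months.

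**The case against.** The strongest reply is that this is a convention declared in advance, not a miscalculation. No figure in the documents fails because of it, and 30.4375 appears nowhere in them. That is right as far as it goes: the rule is open and not invalid. Declaring it does not remove its direction, however, and a closer constant costs nothing.

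Four stronger readings are tempting, and the documents do not support them.
- **That every reported median is overstated.** The SAP gives the medians no unit; one left in days is correct.
- **That every landmark rate is flattered.** The 2-month rate is unchanged. A later rate changes only if an event falls on one of the few added days. Direction is also judged against the mean month: about 2% of possible index dates, in late February 2021, have an actual 2-month span of 59 days. From 4 months on, no calendar span is shorter than the 30-day count.
- **That the rule contradicts the protocol's 7- and 9-month statements.** Step 5 shows that it does not; 212 days even meets 7 months under the 30-day rule and just misses it under 30.4375.
- **That it creates a known mismatch with the Phase 3 trial.** The protocol does not say how that trial converted days, its quoted medians are for overall survival, which is not an endpoint here, and no comparison is planned in the visible text.

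It can also be said that SAP 5.3 replaces a missing day by 1, which moves a partial event date earlier and shortens that duration. This is true, but it affects only incomplete dates, at an unknown frequency, and for a partial chemotherapy start date it lengthens rwPFS-c. It is a separate error, not an offset.

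**Conclusion.** The point holds as a small, one-directional inaccuracy. Any TTF, rwPFS, rwPFS-c or follow-up median expressed in months is 1.46% too long, about 0.09 month at 6 months and 0.18 at 12. The rates from 4 months on are read 1.75 or more days early and are never lower for it.

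The bound of about 0.5 points belongs to the underlying exponential curve. An estimated curve moves in steps, so in one sample the shift is zero or a whole number of events; with an assumed 100 uncensored patients each event is 1/100 = 1 point. Either way it is small beside the half-widths in step 4, and no conclusion of a descriptive study would turn on it. The 1.46% rests only on taking the mean calendar month as the standard.

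**What to change.** In SAP 5.3, replace the 30-day rule by months = days / 30.4375. Use it for all medians and confidence limits given in months and for the 2-monthly landmarks, which then fall at 60.875, 121.75, 182.625 days and so on. In SAP 5.5, state the reporting unit for TTF, rwPFS and rwPFS-c, and in 8.1.1, 8.1.2 and 8.1.4 the unit of the reverse Kaplan–Meier follow-up.

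The cost is one constant in the SAP and the programs, and figures in months that are slightly less favourable. No data collection, endpoint definition or population changes. If output already exists, medians in months can be corrected by multiplying by 30/30.4375 = 0.9856, while the landmark rates need a rerun. If the 30-day rule is kept, it should at least be disclosed beside every result given in months.

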5.4 Steroid equivalent dose (prednisolone-equivalent dose)

The corticosteroid-equivalent dose (prednisolone-equivalent) is calculated as the dose of the starting drug × prednisolone conversion ratio, according to the table below.

General name	Corresponding dose (mg)	Prednisolone conversion ratio
Cortisone	25	0.2
Hydrocortisone	20	0.25
Prednisolone	5	1
Methylprednisolone	4	1.25
Triamcinolone	4	1.25

Dexamethasone	Approximately 0.75	6.67
Betamethasone	Approximately 0.75	6.67

5.5 Derived variable

The items and definitions of variables whose derivation is necessary at the time of statistical analysis are shown below.

Continuous variable

Item	Derivation method
Treatment-free interval: Time from the end date of first-line chemotherapy to the start date of avelumab administration (days)	Start date of initial administration with avelumab – end date of first-line chemotherapy administration + 1
Duration of treatment of first-line chemotherapy (days)	End date of first-line chemotherapy administration – start date of first-line chemotherapy administration + 1
Duration of treatment (irAE treatment) of corticosteroid (days)	End date of corticosteroid administration – start date of corticosteroid administration + 1
Time to treatment failure of avelumab (TTF)	Defined as the period from the date of start of avelumab to the date of end of treatment* for any reasons including death. If there is no record of end of treatment, patients will be censored at the date of last observation during the study period. *The following sensitivity analysis will also be performed. Considering its clinical meaning, "interruption due to being well-controlled" does not correspond to "treatment failure"; it should be treated as an event on the day when the death or discontinuation was observed prior to the last observation date. If no death or discontinuation occurred before the date of the last observation, data will be censored at the date of the last observation.
Real-world progression-free survival (rwPFS)	Defined as the period from the start date of avelumab maintenance therapy to the date of first

	
disease progression (clinical evaluation based on imaging examinations, laboratory tests, and pathological tests, as well as other evaluations by the investigators of each institution) or death from any cause, whichever occurs earlier.
 
If there is no record of death or disease progression, patients on second or later lines (following avelumab maintenance therapy) will be censored at the start of the second-line treatment, and patients on only avelumab maintenance therapy will be censored at the date of the last visit during the study, based on the medical record.

Real-world progression-free survival from chemotherapy (rwPFS-c)	
Defined as the period from the start date of first-line chemotherapy to the date of first disease progression (clinical evaluation based on imaging examinations, laboratory tests, and pathological test, as well as other evaluations by the investigators of each institution) or death from any cause, whichever occurs earlier.
 
If there is no record of death or disease progression, patients on second or later lines (following avelumab maintenance therapy) will be censored at the start of the second-line treatment, and patients on only avelumab maintenance therapy will be censored at the date of the last visit during the study, based on the medical record.

Starting dose of corticosteroid (Steroid equivalent dose)	Calculate according to “5.4 Steroid equivalent dose (prednisolone-equivalent dose.”
Duration of treatment of corticosteroid (days)	Last administration date – date of first administration of the first steroid drug + 1
Duration of treatment of avelumab maintenance (days)	Last administration date – date of first administration + 1.
Duration of treatment of each regimen (days)	Last administration date – date of first administration + 1.

Categorical variable

Item	Derivation method
Age (2 divisions)	Age is divided into the following categories: <65 years/65 years or older
Site of primary tumor (2 divisions)	The primary site is divided into the following categories: "upper urinary tract" for renal pelvis or ureter "lower urinary tract" for bladder and urethra
Tumor histological type (2)	The histological types are divided into the following categories. "Urothelial carcinoma" for urothelial carcinoma "Non-urothelial carcinoma" for adenocarcinoma, squamous cell carcinoma, small cell carcinoma, or others
Presence or absence of visceral metastasis	"Presence" will be selected if the metastatic site is "lung," "liver," "adrenal gland," "pancreas," "kidney," "spleen," or "other" which is regarded as visceral metastasis. If the metastatic site is not regarded as visceral metastasis, "absence" will be selected.
Presence or absence of non-visceral metastasis	"Presence" will be selected if the metastatic site is "bone," "distant lymph nodes," or "other" which is regarded as non-visceral metastasis. If the metastatic site is not regarded as non-visceral metastasis, "absence" will be selected.
ECOG Performance Status at start of first-line chemotherapy (1) *For at the start of avelumab administration, "at the start of first-line chemotherapy administration" should be read as "at the start of avelumab administration."	ECOG Performance Status at start of first-line chemotherapy is categorized as follows. 0/1 or higher
Performance Status at start of first-line chemotherapy (2) *For at the start of avelumab	ECOG Performance Status at start of first-line chemotherapy is categorized as follows. 0/1/2 or higher

administration, " at the start of first-line chemotherapy administration" should be read as "at the start of avelumab administration."																																													
Number of cycles in first-line chemotherapy (3 divisions)	Number of cycles in first-line chemotherapy is divided into the following categories. 3 or less/4 to 6/7 or more																																												
Karnofsky performance status (2 divisions)	Karnofsky performance status is divided into the following categories. <80%/>=80%																																												
Bajorin risk classification	Bajorin risk classification is categorized as follows based on the number of risk factors. <Risk factors> 
• Visceral metastasis is "present"• Karnofsky performance status is "<80%" If there is no risk factor, "0 (no risk factor)". If there is one risk factor, "1 (single risk factor)". If there are two risk factors, "2 (two risk factors)".																																												
Clinical stage classification: Bladder	Clinical stage is categorized using primary tumor (T factor), regional lymph nodes (N factor), distant metastasis (M factor) as follows. 
  
 Primary tumor (T factor)	Regional lymph nodes (N factor)	Distant metastasis (M factor)	Clinical stage	
   
 Ta	N0	M0	0a	
 
 Tis	N0	M0	0is	
 
 T1	N0	M0	I	
 
 T2a, T2b	N0	M0	II	
 
 T3a, T3b, T4a	N0	M0	IIIA	
 
 T1, T2a, T2b, T3a, T3b, T4a	N1	M0	IIIA	
 
 T1, T2a, T2b, T3a, T3b, T4a	N2, N3	M0	IIIB	
 
 T4b	Any N	M0	IVA	
 
 Any T	Any N	M1a	IVA	
 
 Any T	Any N	M1b	IVB	
  
	Primary tumor (T factor)	Regional lymph nodes (N factor)	Distant metastasis (M factor)	Clinical stage	Ta	N0	M0	0a	Tis	N0	M0	0is	T1	N0	M0	I	T2a, T2b	N0	M0	II	T3a, T3b, T4a	N0	M0	IIIA	T1, T2a, T2b, T3a, T3b, T4a	N1	M0	IIIA	T1, T2a, T2b, T3a, T3b, T4a	N2, N3	M0	IIIB	T4b	Any N	M0	IVA	Any T	Any N	M1a	IVA	Any T	Any N	M1b	IVB
Primary tumor (T factor)	Regional lymph nodes (N factor)	Distant metastasis (M factor)	Clinical stage																																										
Ta	N0	M0	0a																																										
Tis	N0	M0	0is																																										
T1	N0	M0	I																																										
T2a, T2b	N0	M0	II																																										
T3a, T3b, T4a	N0	M0	IIIA																																										
T1, T2a, T2b, T3a, T3b, T4a	N1	M0	IIIA																																										
T1, T2a, T2b, T3a, T3b, T4a	N2, N3	M0	IIIB																																										
T4b	Any N	M0	IVA																																										
Any T	Any N	M1a	IVA																																										
Any T	Any N	M1b	IVB																																										
Clinical stage classification:	Clinical stage is categorized using primary tumor (T																																												

Urethra	factor), reginal lymph nodes (N factor), distant metastasis (M factor) as follows.			
	Primary tumor (T factor)	Reginal lymph nodes (N factor)	Distant metastasis (M factor)	Clinical stage
	Ta	N0	M0	0a
	Tis	N0	M0	0is
	T1	N0	M0	I
	T2	N1	M0	II
	T1, T2	N1	M0	III
	T3	N0, N1	M0	III
	T4	N0, N1	M0	IV
Clinical stage classification: Renal pelvis, Ureter	Any T	N2	M0	IV
	Any T	Any N	M1	IV
	Clinical stage is categorized using primary tumor (T factor), reginal lymph nodes (N factor), distant metastasis (M factor) as follows.			
	Primary tumor (T factor)	Reginal lymph nodes (N factor)	Distant metastasis (M factor)	Clinical stage
	Ta	N0	M0	0a
	Tis	N0	M0	0is
	T1	N0	M0	I
	T2	N0	M0	II
	T3	N0	M0	III
Treatment-free interval: Time from the end date of first-line chemotherapy to the start date of avelumab administration (3 divisions)	T4	N0	M0	IV
	Any T	N1、N2	M0	IV
	Any T	Any N	M1	IV
Response (avelumab maintenance)	Time from the end date of first-line chemotherapy to the start date of avelumab administration is divided into the following categories. <4 weeks/4 to 10 weeks/>10 weeks			
	Determination of the best overall response to avelumab maintenance is categorized as following: "Objective response" when "CR" or "PR." "Non-objective response" when "SD" or "PD"			
	Determination of the best overall response to first-line chemotherapy is categorized as following:			

	
"Objective response" when "CR" or "PR."
 
"Non-objective response" when "SD" or "PD"

Best overall response to first-line chemotherapy (2)	Determination of the best overall response to first-line chemotherapy is categorized as following: CR + PR/SD
Presence or absence of prednisolone	"Presence" will be selected when "prednisolone" is selected for the corticosteroid administration drug name, and "absence" will be selected when "No" is selected for the drug name.
Presence or absence of methylprednisolone	"Presence" will be selected when "methylprednisolone" is selected for the corticosteroid administration drug name, and "absence" will be selected when "No" is selected for the drug name.
Presence or absence of betamethasone	"Presence" will be selected when "betamethasone" is selected for the corticosteroid administration drug name, and "absence" will be selected when "No" is selected for the drug name.
Presence or absence of dexamethasone	"Presence" will be selected when "dexamethasone" is selected for the corticosteroid administration drug name, and "absence" will be selected when "No" is selected for the drug name.
Presence or absence of hydrocortisone	"Presence" will be selected when "hydrocortisone" is selected for the corticosteroid administration drug name, and "absence" will be selected when "No" is selected for the drug name.
Presence or absence of others	"Presence" will be selected when "other" is selected for the corticosteroid administration drug name, and "absence" will be selected when "No" is selected for the drug name.
Presence or absence of treatment with non-high-dose corticosteroid	"Absence" will be selected if the prednisolone-equivalent starting dose is 40 mg or higher. "Presence" will be selected if it is less than 40 mg.
Presence or absence of treatment with high-dose corticosteroid	"Absence" will be selected if the prednisolone-equivalent starting dose is less than 40 mg. "Presence" will be selected if it is 40 mg or higher.

Presence or absence of steroid pulse therapy	"Absence" will be selected if the prednisolone-equivalent starting dose is less than 625 mg. "Presence" will be selected if it is 625 mg or higher.
NLR	Neutrophil count (/ μ L)/lymphocyte count (/ μ L)
Hematological test (Red blood cell count, hemoglobin, hematocrit, white blood cell count, neutrophil count, eosinophil, basophil, monocyte, lymphocyte, platelet count, CRP, total protein, albumin, AST, ALT, LDH, BUN, creatinine, Na, K, Cl, NLR (2 divisions))	Hematological test (Red blood cell count, hemoglobin, hematocrit, white blood cell count, neutrophil count, eosinophil, basophil, monocyte, lymphocyte count, platelet count, CRP, total protein, albumin, AST, ALT, LDH, BUN, creatinine, Na, K, Cl, NLR) is categorized as following: < median/ \geq median
Hemoglobin (g/dL) (2)	Hemoglobin is divided into the following categories: <10 g/dL/ \geq 10 g/dL
White blood cell count (2)	White blood cell count is divided into the following categories: <8000/ μ L/ \geq 8000/ μ L
NLR (2)	NLR is divided into the following categories: <3/ \geq 3
NLR (3)	NLR at the start of the first-line chemotherapy and at the start of first cycle of avelumab is divided into the following categories, regarding NLR at the start of first cycle of avelumab as a starting point. "Low \rightarrow Low" when changed from NLR <3 (Low) to NLR <3 (Low), "Low \rightarrow High" when changed from NLR <3 (Low) to NLR \geq 3 (High), "High \rightarrow Low" when changed from NLR \geq 3 (High) to NLR <3 (Low), "High \rightarrow High" when changed from NLR \geq 3 (High) to NLR \geq 3 (High)

